1. PROTOCOL SUMMARY

1.1. Synopsis

Rationale:

RSV MAT-004 will evaluate, for the first time:

- The safety, reactogenicity, and immunogenicity of the investigational RSV maternal vaccine when administered to healthy women in the third trimester of pregnancy, and
- The effects of maternal immunization on the infants born to these vaccinated women.

A Phase I/II study of this vaccine is underway in healthy *non-pregnant* women (study RSV MAT-001; NCT02753413). The 2 dose levels considered to have the highest immunogenicity associated with an acceptable safety profile in RSV MAT-001 (60 and 120 µg) will be further investigated in the current study (RSV MAT-004).

RSV MAT-004 will only be initiated after a favorable evaluation of all available safety data from completed/ongoing non-clinical studies and from the ongoing RSV MAT-001 study.

Objectives and Endpoints are presented in [Table 5](#).

1.2. Schema

This is a multi-center, randomized, observer-blinded, placebo-controlled study. *Up to* 300 healthy maternal subjects 18 to 40 years of age (inclusive, at the time of informed consent) will be assigned to one of 3 study groups, and will receive a single intramuscular injection between 28^{0/7} to 33^{6/7} weeks of gestation (inclusive) as follows:

- RSVPreF3, 60 µg (N up to ~ 100),
- RSVPreF3, 120 µg (N up to ~ 100), or
- Saline placebo (N up to ~ 100).

Maternal subjects will participate for approximately 9 months (from informed consent until 6 months after delivery), and will be evaluated for reactogenicity, safety, and humoral immune response (including maternal – infant RSV-specific antibody transfer). Infant subjects will be followed for 12 months after birth and will be evaluated for safety and RSV-specific antibody levels. All safety data will be reviewed by a blinded Safety Review Team (SRT) and an unblinded Independent Data Monitoring Committee (IDMC) on an on-going basis.

Section [4.1](#) provides an overview of the study design; Section [8.2.3](#) presents additional information about study holding rules and safety monitoring.

CONFIDENTIAL209544 (RSV MAT-004)
Protocol Amendment 3 Final**1.3. Schedules of Activities (SoA)**

For maternal subjects, [Table 1](#) presents the Schedule of Activities (SoA) and [Table 2](#) describes the allowed study visit intervals. For infant subjects, [Table 3](#) presents the SoA and [Table 4](#) describes the allowed study visit intervals.

Whenever possible, the investigator should arrange study visits within the allowed study visit intervals. Immunogenicity data from blood samples collected outside an allowed interval may not be considered in the associated per protocol set (PPS) for analysis.

Please note:

- Study visits, assessments and procedures do not replace local standards of care. If local standard of care recommends additional visits/medical evaluations (for maternal subjects or their infants), subjects should comply with these local recommendations.
- Any adverse event / potential adverse event identified during a study visit or procedure should be treated according to local standards of care or by referral to an appropriate health care provider
- When a maternal subject completes Visit 1 (enrolment), and again at Visit 5 (delivery), site staff should ensure all site study obstetrician(s) and pediatrician(s) are informed. This will help to ensure that study pediatrician(s) and/or staff are aware of the maternal subject's approximate date of delivery and potential enrolment of the neonate.
- Maternal subject Visits 2 (day 8), 3 (day 31), 4 (Day 61), 7 (Day 121 post delivery) and 8 (Day 181 post delivery) and infant subject Visits 1-NB through 5-NB (birth to 12 months after birth) may be conducted through a home visit by qualified site staff (or a designated third party), as appropriate per the judgment of the investigator (and as allowed by local law).
- Respiratory tract illness (RTI) assessment visits and event-driven safety visits may take place at the investigator's clinical facility or another medical facility, or via a home visit by qualified site staff (or a designated third party), as appropriate per the judgment of the investigator (and as allowed by local law).
- The visit location must have appropriate infrastructure and logistics to support completion of all study procedures. Blood samples must be centrifuged within 1 hour after collection if used to assess biochemistry, or within 2 hours of collection if used to assess hematology or immune response.
- Contact may be via telephone, SMS, email or other means (including videotelephony or telemedicine), depending on local best practice. If the study site is the subject's primary healthcare facility, contact with study personnel may also be made in the context of a visit for routine or event-driven care.
- Refer to [Section 8](#) for information about special circumstances (e.g., the COVID 19 pandemic) and their impact on study activities.

CONFIDENTIAL

209544 (RSV MAT-004)
Protocol Amendment 3 Final**Table 1 Schedule of activities for maternal subjects**

| Epochs | Epoch 001 | Epoch 002 | | | | | | | | | | Additional Information | | |
|---|------------|--|--|-----|-----|------------------|-----------|--|------------|------------------|---------------------|------------------------|--|--------------------------------|
| | | | May be replaced by V5, depending on delivery date | | | | | To coincide with infant visits 2-NB, 3-NB, 4-NB | | | Event Driven | | | |
| Visit / Contact | Screening | V1 | V2 | V3 | V4 | V5 | V6 | V7 | V8 | Monthly contacts | Safety Visit | MA-RTI Visit | For monthly contacts: Table 2 & Section 8.4.2 . After delivery, maternal & infant monthly contacts coincide. | |
| Gestational Age (GA) | | 28 ^{0/7} - 33 ^{6/7} | | | | | | | | | | | | |
| Visit Day | D-28 – D-1 | D1 | D8 | D31 | D61 | Delivery D1PD | D43 PD | D121 PD | D181 PD | | | | | |
| Informed consent | • | | | | | | | | | | | | | Section 10.1.3 |
| Check Inclusion/exclusion criteria | • | 0 | | | | | | | | | | | Sections 5.1.1 , 5.2.1 | |
| Assign maternal subject study number | • | | | | | | | | | | | | Section 6.3.1 | |
| Assign infant subject study number | | 0 | | | | | | | | | | | | |
| Record Demographic data and lifestyle characteristics | • | | | | | | | | | | | | Section 8.2.1.1.1 | |
| Review & collect Medical and vaccination history | • | 0 | | | | | | | | | | | Section 8.2.1.1.2 | |
| Record outcome of Level 2 ultrasound (also known as a fetal anomaly ultrasound scan or fetal morphology assessment) | • | | | | | | | | | | | | | |
| Record obstetric history from past and current pregnancies | • | | | | | | | | | | | | | |

CONFIDENTIAL

209544 (RSV MAT-004)
Protocol Amendment 3 Final

| Epochs | Epoch 001 | Epoch 002 | | | | | | | | | | Additional Information | | |
|--|------------|---------------------------------------|--|-----|-----|---------------|--|---------|---------|------------------|---------------------|------------------------|--|--|
| | | | May be replaced by V5, depending on delivery date | | | | To coincide with infant visits 2-NB, 3-NB, 4-NB | | | | Event Driven | | | |
| Visit / Contact | Screening | V1 | V2 | V3 | V4 | V5 | V6 | V7 | V8 | Monthly contacts | Safety Visit | MA-RTI Visit | For monthly contacts: Table 2 & Section 8.4.2. After delivery, maternal & infant monthly contacts coincide. | |
| Gestational Age (GA) | | 28 ^{0/7} - 33 ^{6/7} | | | | | | | | | | | | |
| Visit Day | D-28 – D-1 | D1 | D8 | D31 | D61 | Delivery D1PD | D43 PD | D121 PD | D181 PD | | | | | |
| Record Travel history to or living in Zika virus endemic countries/regions | • | • | • | • | • | • | | | | | | | During the current pregnancy only | |
| General and obstetrical examination | • | • | • | • | • | • | • | • | • | | 0 | 0 | General exam is symptom directed at V7, V8, & event-driven visits. Vaginal exams are symptom directed. See Section 8.2.1.2 | |
| Pre-vaccination body temperature | | • | | | | | | | | | | | Preferred location for measurement will be the oral cavity. "Fever" = temperature ≥38.0°C/100.4°F regardless of the location of measurement. | |
| Urine sample | • | • | • | • | • | | | | | | | | Table 11 | |

CONFIDENTIAL

209544 (RSV MAT-004)
Protocol Amendment 3 Final

| Epochs | Epoch 001 | Epoch 002 | | | | | | | | | | Additional Information | | |
|---|------------|---------------------------------------|--|-----|-----|---------------|--|---------|---------|------------------|---------------------|------------------------|--|--|
| | | | May be replaced by V5, depending on delivery date | | | | To coincide with infant visits 2-NB, 3-NB, 4-NB | | | | Event Driven | | | |
| Visit / Contact | Screening | V1 | V2 | V3 | V4 | V5 | V6 | V7 | V8 | Monthly contacts | Safety Visit | MA-RTI Visit | For monthly contacts: Table 2 & Section 8.4.2. After delivery, maternal & infant monthly contacts coincide. | |
| Gestational Age (GA) | | 28 ^{0/7} - 33 ^{6/7} | | | | | | | | | | | | |
| Visit Day | D-28 – D-1 | D1 | D8 | D31 | D61 | Delivery D1PD | D43 PD | D121 PD | D181 PD | | | | | |
| Blood sample (hematology / biochemistry, ~ 5.5 ml) | • | • | • | | | | | | | | • | | Table 11 If screening sample ≤ 15 days before V1, then V1 sample not required. During an event-driven safety visit, additional samples are per investigator's discretion and standard of care and to be tested locally. | |
| Blood sample (hematocrit: ~ 3.0 ml) | | | | • | | • | • | | | | | | Table 11 | |
| Blood sample (immunogenicity ~ 10 ml) | | • | | • | | • | • | | | | | | | |
| Cord blood (~ 5 to 10 ml) | | | | | | • | | | | | | | | |
| Nasal swab | | | | | | | | | | | | • | | |
| Check contraindications to and criteria for temporary delay for vaccination | | 0 | | | | | | | | | | | Sections 5.2.1 and 7.1.1 | |

CONFIDENTIAL

209544 (RSV MAT-004)
Protocol Amendment 3 Final

| Epochs | Epoch 001 | Epoch 002 | | | | | | | | | | Additional Information | | |
|--|------------|---------------------------------------|---|-----|-----|---------------|--------|--|---------|------------------|--------------|------------------------|--|--|
| | | | May be replaced by V5, depending on delivery date | | | | | To coincide with infant visits 2-NB, 3-NB, 4-NB | | | | | Event Driven | |
| Visit / Contact | Screening | V1 | V2 | V3 | V4 | V5 | V6 | V7 | V8 | Monthly contacts | Safety Visit | MA-RTI Visit | For monthly contacts: Table 2 & Section 8.4.2 . After delivery, maternal & infant monthly contacts coincide. | |
| Gestational Age (GA) | | 28 ^{0/7} - 33 ^{6/7} | | | | | | | | | | | | |
| Visit Day | D-28 – D-1 | D1 | D8 | D31 | D61 | Delivery D1PD | D43 PD | D121 PD | D181 PD | | | | | |
| Allocate maternal study group, intervention number | | 0 | | | | | | | | | | | Sections 6.3.2 and 6.3.3 | |
| Assign cohort for blood sampling of infants | | 0 | | | | | | | | | | | | |
| Administer Intervention (study vaccine/product) | | • | | | | | | | | | | | Sections 6.1 and 6.2 | |
| Record administered intervention number | | • | | | | | | | | | | | | |
| Observe for 60 minutes post-dose | | 0 | | | | | | | | | | | | |
| Distribute maternal subject card | 0 | 0 | | | | | | | | | | | At screening or at Visit 1 as per local practice. Section 8.3.4 | |
| Record Labor / Delivery information | | | | | | • | | | | | | | | |
| Record pregnancy / delivery outcomes | | | | | | • | | | | | | | Submit Expedited AE report for an adverse pregnancy outcome (Section 8.3.3) | |
| Train maternal subject /LAR on use of e-diary device | | 0 | 0 | | | | | | | | | | Sections 8.4.2 and 10.3.8 | |

CONFIDENTIAL

209544 (RSV MAT-004)
Protocol Amendment 3 Final

| Epochs | Epoch 001 | Epoch 002 | | | | | | | | | | | Additional Information | |
|---|------------|---------------------------------------|---|-----|-----|---------------|--------|--|---------|------------------|--------------|--------------|---|--------------|
| | | | May be replaced by V5, depending on delivery date | | | | | To coincide with infant visits 2-NB, 3-NB, 4-NB | | | | | | Event Driven |
| Visit / Contact | Screening | V1 | V2 | V3 | V4 | V5 | V6 | V7 | V8 | Monthly contacts | Safety Visit | MA-RTI Visit | For monthly contacts: Table 2 & Section 8.4.2. After delivery, maternal & infant monthly contacts coincide. | |
| Gestational Age (GA) | | 28 ^{0/7} - 33 ^{6/7} | | | | | | | | | | | | |
| Visit Day | D-28 – D-1 | D1 | D8 | D31 | D61 | Delivery D1PD | D43 PD | D121 PD | D181 PD | | | | | |
| Distribute e-diary device to maternal subject / LAR. | | 0 | | | | | | | | | | | | |
| Review e-diary results | | 0 | 0 | 0 | 0 | 0 | 0 | 0 | 0 | | | | | |
| Return e-diary device | | | | | | | | | 0 | | | | At V8 or infant Visit 4-NB, whichever is last. | |
| Concomitant medications / vaccinations | | • | • | • | • | • | • | • | • | • | • | • | Sections 6.5.1, 6.5.3 | |
| Solicited administration site & systemic events (Days 1 to 7) | | • | • | | | | | | | | | | Sections 10.3.3, 10.3.8 | |
| All unsolicited AEs (Days 1 to 30) | | • | • | • | | | | | | • | • | | Sections 10.3.4, 10.3.8 | |
| Pregnancy-related AESIs | | • | • | • | • | • | • | | | • | • | • | Sections 8.3.3.2, 10.3.8 | |
| Suspected, probable and confirmed cases of COVID-19 infection | | • | • | • | • | • | • | • | • | • | • | • | Section 8.3.2.1 | |
| MAEs | | • | • | • | • | • | • | • | • | • | • | | Sections 8 and 10.3.9.3 | |
| MA-RTI signs, symptoms and corresponding (S)AEs | | | | | | | | | | • | | • | Sections 8.3.3, 8.4 | |

CONFIDENTIAL

209544 (RSV MAT-004)
Protocol Amendment 3 Final

| Epochs | Epoch 001 | Epoch 002 | | | | | | | | | | | Additional Information | |
|--|------------|---------------------------------------|---|-----|-----|---------------|--------|--|---------|------------------|--------------|--------------|---|--------------|
| | | | May be replaced by V5, depending on delivery date | | | | | To coincide with infant visits 2-NB, 3-NB, 4-NB | | | | | | Event Driven |
| Visit / Contact | Screening | V1 | V2 | V3 | V4 | V5 | V6 | V7 | V8 | Monthly contacts | Safety Visit | MA-RTI Visit | For monthly contacts: Table 2 & Section 8.4.2. After delivery, maternal & infant monthly contacts coincide. | |
| Gestational Age (GA) | | 28 ^{0/7} - 33 ^{6/7} | | | | | | | | | | | | |
| Visit Day | D-28 – D-1 | D1 | D8 | D31 | D61 | Delivery D1PD | D43 PD | D121 PD | D181 PD | | | | | |
| SAEs, and AEs leading to study withdrawal | | • | • | • | • | • | • | • | • | • | • | | Sections 7.2, 10.3.8 | |
| SAEs related to study participation or concurrent GSK medication/vaccine | • | • | | | | | | | | | | | Sections 8.3.3, 10.3.8 | |
| Subsequent pregnancies | | | | | | | • | • | • | • | • | | Section 10.3.8 | |
| Record interest in joining future extension study | | | | | | | | ○ | • | | | | Request at Visit 7, confirm at Visit 8; Section 6.7 | |
| Screening conclusion | • | | | | | | | | | | | | | |
| Investigator sign-off on eCRF before analysis | • | | | • | | | • | | • | | | | | |
| Study conclusion | | | | | | | | | • | | | | Section 4.4 | |

The timing of an event-driven site visit (e.g., to further evaluate a potential AE or MA-RTIs) cannot be defined with precision in the protocol. Event-driven visits may occur throughout the study. **Note:** • is used to indicate a study procedure that requires documentation in the individual eCRF. ○ is used to indicate a study procedure that does not require documentation in the individual eCRF. V = visit; D = day; GA = gestational age; MA-RTI = medically attended respiratory tract illness; PD = post delivery; Hct = hematocrit.

CONFIDENTIAL209544 (RSV MAT-004)
Protocol Amendment 3 Final**Table 2 Intervals between study visits – maternal subjects**

| Interval | Optimal interval | Allowed interval | Additional Information |
|------------------|----------------------------------|--------------------------------------|---|
| Screening → V1 | 4 days | 1– 28 days | The screening interval extends from Day -28 to Day -1 (the day before dosing). If a subject is screened but not vaccinated within the allowed interval, a re-screening can be done to establish the subject's eligibility. Please make sure the subject's gestational age is still within the allowed range, refer to Section 10.7 for guidance on gestational age assessment. |
| V1 → V2 | 7 days | 7 – 14 days | |
| V1 → V3 | 30 days | 20 - 45 days | |
| V1 → V4 | 60 days | 50–75 days | |
| V5 (delivery) | 0 days | 1 day before to 3 days post delivery | Collect maternal blood sample at any point from the day before up to delivery. If blood is not collected during delivery, collect maternal blood sample no later than 3 days after delivery. A cord blood sample should be collected at the time of each delivery. If cord blood cannot be collected at delivery, a blood sample should be collected from the infant subject as soon as possible and no later than 3 days after birth. |
| V5 → V6 | 42 days | 40 – 60 days | |
| V5 → V7 | 120 days | 110 -140 days | Visit may coincide with infant subject's routine vaccination visit if consistent with the participating country's routine infant vaccination schedule) |
| V5 → V8 | 180 days | 165 – 200 days | |
| Monthly contacts | Approximately every 25 – 35 days | | Monthly until Visit 8. May occur more often between Visit 5 and Visit 6 at the discretion of study personnel. Contacts are additional to and do not replace protocol specified Visits. |

V=Visit

CONFIDENTIAL

209544 (RSV MAT-004)
Protocol Amendment 3 Final**Table 3 Schedule of activities for infants**

| Epochs | Epoch 002 | | | | | | Epoch 003 | | Additional Information |
|---|-----------|---|----------|----------|------------------|---------------------|-----------|-----------|--|
| | | To coincide with maternal visits 6, 7, 8 | | | | Event-Driven | | | |
| Visit / Contact | V1-NB | V2-NB | V3-NB | V4-NB | Monthly contacts | RTI Visit | C1-NB | V5-NB | NB=Newborn Monthly Contacts coincide with maternal monthly contacts. RTI Visit: Sections 8.4.3 and 8.4.5. |
| Age of infant | | 6 weeks | 4 months | 6 months | | | 9 months | 12 months | |
| Visit Day | Birth | D43 | D121 | D181 | | | D271 | D365 | Table 4 |
| Check Inclusion / exclusion criteria | • | | | | | | | | Sections 5.1.2 , 5.2.2 |
| Re-consent if required by local regulations | • | | | | | | | | |
| Record infant subject study number | • | | | | | | | | |
| Record subcohort for immunogenicity blood sampling | • | | | | | | | | Section 6.3.3 |
| Distribute infant's subject card | 0 | | | | | | | | Section 8.3.4 |
| Demographic data and lifestyle characteristics | • | • | • | • | | | • | • | Section 8.2.2.1 , Record at Visit 1-NB and if changes in lifestyle characteristics thereafter |
| Apgar score | • | | | | | | | | At 1, 5 and 10 minutes, if available |
| Weight, length, head circumference, physical examination | • | • | • | • | | | | • | Section 8.2.2.2 |
| Blood sample if no cord blood ~2.5 ml | • | | | | | | | | Adjust volume if weight ≤ 2.5 Kg. Refer to Table 12 . |
| Blood sample (immunology, infants) ~2.5 ml | | • | • | • | | | | | 1 sample at one of these visits, as per infant's assigned subcohort. Adjust volume if weight ≤ 2.5 Kg. Refer to Table 12 |
| Concomitant medications / vaccinations | • | • | • | • | • | • | • | • | Sections 6.5.2 , 6.5.3 |
| Neonatal AESIs | • | • | | | | | | | Sections 8.3.3 , 10.3.8 . Must submit an Expedited AE Report |
| Suspected, probable and confirmed cases of COVID-19 infection | • | • | • | • | • | • | • | • | |

CONFIDENTIAL

209544 (RSV MAT-004)
Protocol Amendment 3 Final

| Epochs | Epoch 002 | | | | | | Epoch 003 | | Additional Information |
|--|-----------|---|----------|----------|------------------|---------------------|-----------|-----------|--|
| | | To coincide with maternal visits 6, 7, 8 | | | | Event-Driven | | | |

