2.3. Benefit/Risk assessment

Detailed information about the known and expected benefits and risks and reasonably expected adverse events of the RSV Maternal (RSVPreF3) vaccine can be found in the IB.

CONFIDENTIAL209544 (RSV MAT-004)
Protocol Amendment 3 Final

The balance of anticipated benefits and apparent risks associated with the RSV maternal (RSVPreF3) vaccine continues to be acceptable following ongoing systematic review of the safety data.

3. OBJECTIVE(S) AND ENDPOINT(S)**Table 5 Study objectives and endpoints**

| Primary Safety objectives | Primary Safety endpoint(s) |
|--|--|
| To evaluate the safety and reactogenicity of a single IM dose of study vaccine administered to maternal subjects, from Visit 1 up to 6 weeks after delivery | Occurrence of solicited administration site and systemic events) during a 7-day follow-up period after vaccination (i.e. the day of vaccination and 6 subsequent days). |
| | Occurrence of any hematological (complete blood count with differential and platelet count) or biochemical (alanine amino-transferase, aspartate amino-transferase, creatinine, blood urea nitrogen) laboratory abnormality at baseline (up to 15 days before vaccination) and Day 8 (Visit 2) |
| | Occurrence of unsolicited AEs that occur during a 30-day follow-up period after vaccination (i.e. the day of vaccination and 29 subsequent days). |
| | Occurrence of serious adverse events (SAEs), AEs leading to study withdrawal, and medically attended AEs (MAEs) from Visit 1 (Day 1) up to 6 weeks after delivery (Day 43 post-delivery, Visit 6). |
| To evaluate pregnancy outcomes and pregnancy-related AESIs after a single IM dose of study vaccine administered to maternal subjects, from Visit 1 up to 6 weeks after delivery (Visit 6). | Pregnancy outcomes from Day 1 (Visit 1) up to 6 weeks after delivery (Day 43 post-delivery, Visit 6). These include live birth with no congenital anomalies, live birth with congenital anomalies, fetal death/still birth (antepartum or intrapartum) with no congenital anomalies, fetal death/still birth (antepartum or intrapartum) with congenital anomalies, elective/therapeutic termination with no congenital anomalies and elective/therapeutic termination with congenital anomalies. |

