8.1.1. Biological samples

Samples will not be labelled with information that directly identifies the subject but will be coded with the identification number for the subject (subject number).

CONFIDENTIAL

209544 (RSV MAT-004)
Protocol Amendment 3 Final**Table 11 Biological samples – maternal subjects**

| Maternal Sample type | Collected to Evaluate | Minimum Quantity per subject | Unit | Time point | Additional Information |
|----------------------|---|------------------------------|---|--------------------------------|---|
| Whole Blood | Hematology, Biochemistry | ~5.5 | ml | Screening | As needed to achieve up to 300 eligible subjects at Visit 1. |
| | Hematology, Biochemistry Immune response | ~15.5* | ml | Visit 1 (Day 1) | Hematology, chemistry: ~5.5 ml. This sample is NOT required if the screening sample was collected ≤15 days before Visit 1. Immune response: ~10 mL. Must be collected at Visit 1 before dosing. *Volume of sample collected to assess immune response may be reduced to ~5 ml at investigator's discretion. Refer to the Laboratory Manual. |
| | Hematology, Biochemistry | ~5.5 | ml | Visit 2(Day 8) | |
| | Hematocrit Immune response | ~13* | ml | Visit 3 (Day 31) | Hematocrit: ~3 mL Immune response: ~10 mL. *Volume of sample collected to assess immune response may be reduced to ~5 ml at investigator's discretion. Refer to the Laboratory Manual. |
| | | ~13* | ml | Visit 5 (Delivery) | |
| | | ~13* | ml | Visit 6 (Day 43 post delivery) | |
| | ~65.5 | ml | Minimum Total, not including repeat or unscheduled samples | | |
| Cord blood | Immune Response | ~5, up to ~10 | ml | Visit 5 (Delivery) | |
| Urine | Protein, Glucose | Dipstick | NA | Screening | As needed to achieve up to 300 eligible subjects at Visit 1. |
| | | | | Visit 1 (Day 1) | |
| | | | | Visit 2 (Day 8) | |
| | | | | Visit 3 (Day 31) | |
| | | | | Visit 4 (Day 61) | |
| Nasal Swab | Presence of:RSV A / B | - | - | MA RTI Assessment Visit | Collect a nasal swab from any maternal subject who reports a medically attended (MA) RTI |

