9.4.3. Primary endpoints

9.4.3.1. Safety

| Primary Safety Endpoints | | Statistical Analysis Methods |
|--------------------------|--|--|
| Maternal subjects | Occurrence of Solicited administration site and systemic events during a 7-day follow-up period after vaccination (i.e. the day of vaccination and 6 subsequent days). | 
The number and percentage with exact 95% CI of maternal subjects reporting each Solicited administration site event (any grade, each grade,) and solicited systemic event (any, each grade) during the 7-day (days 1 to 7) follow-up period after vaccination will be tabulated by maximum intensity per subject for each study vaccine group.
 
For fever during the 7-day follow-up period after vaccination, the number and percentage of maternal subjects reporting any fever (i.e., temperature ≥ 38 °C) and fever by half degree (°C) cumulative increments, any Grade 3 fevers, will be reported. In addition, the prevalence of any and Grade 3 fever will be presented graphically over time after vaccination.
 
The number and percentage of maternal subjects with at least one administration site AE (solicited and unsolicited), with at least one systemic AE (solicited and unsolicited) and with any AE during the 7-day follow-up period after vaccination will be tabulated with exact 95% confidence interval (CI) by group. The same computations will be done for Grade 3 solicited and unsolicited AEs, for any AEs considered related to vaccination, for any Grade 3 AEs considered related to vaccination and for any AEs resulting in a medically attended visit (i.e., MAEs).
 |
| | Occurrence of any protocol-specified hematological or biochemical laboratory abnormality at baseline (up to 15 days before vaccination) and Day 8 (Visit 2) | The number and percentage of subjects with hematology and biochemistry results outside central laboratory normal ranges will be tabulated to show Day 8 versus baseline. The maximum grading as described in [Sheffield, 2013] and in the SPM from Screening up to Day 8 will also be tabulated. |

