10.2. Appendix 2: Clinical laboratory tests

Study-required laboratory assessments detailed in [Table 26](#), except urinalysis, should be performed by a central laboratory. During special circumstances, hematocrit may be performed locally if it is not possible to collect a blood sample for central analysis using GSK-provided supplies (see [Section 8](#)).

CONFIDENTIAL209544 (RSV MAT-004)
Protocol Amendment 3 Final**Table 26 Protocol-Required Safety Laboratory Assessments**

| Laboratory Assessments | Parameters |
|------------------------|---|
| Hematology | Leukocytes (White Blood Cells) |
| | Lymphocytes |
| | Neutrophils |
| | Eosinophils |
| | Platelets |
| | Erythrocytes (Red Blood Cells) |
| | Hematocrit |
| | Hemoglobin |
| | Erythrocyte Mean Corpuscular Volume (MCV) |
| | Aspartate Aminotransferase (AST) / Serum Glutamic-Oxaloacetic Transaminase (SGOT) |
| | Alanine Aminotransferase (ALT) / Serum Glutamic-Pyruvic Transaminase (SGPT) |
| | Creatinine |
| | Urea nitrogen |
| | Urinalysis by dipstick |
| Protein | |

Assessment of eligibility and grading of laboratory parameters will be based on reference ranges described in [Sheffield, 2013] and the SPM for this study.

10.3. Appendix 3: Adverse Events: definitions and procedures for recording, evaluating, follow-up, and reporting

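### The Section 1.3 handling note requires hematology samples to be centrifuged, which does not fit the cell-based panel in Table 26 and should be corrected

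*Protocol*

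**What the plan says.** Protocol Section 1.3 (Schedules of Activities) has a note on visit locations that also fixes sample processing. It reads "Blood samples must be centrifuged within 1 hour after collection if used to assess biochemistry", and the same sentence continues "or within 2 hours of collection if used to assess hematology or immune response". The note applies wherever a visit takes place.

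The hematology results are used in three places:

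- **Primary safety endpoint.** Table 5 (Section 3) includes "Occurrence of any hematological (complete blood count with differential and platelet count) or biochemical" laboratory abnormality at baseline and Day 8. Section 9.4.3.1 adds that "results outside central laboratory normal ranges will be tabulated to show Day 8 versus baseline", and that the maximum grade up to Day 8 is also tabulated.
- **Eligibility.** Section 5.2.1.1 excludes women with Grade 2 or higher hematological abnormalities at screening, and those with Grade 1 abnormalities judged clinically significant.
- **Holding rule 2c.** Table 18 counts Grade 3 hematological or biochemical abnormalities at Day 8 in the active vaccine groups.

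Section 8.1.4 makes both the clinical laboratory manual and Section 1.3 binding for the safety laboratory tests.

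**The concern.** Centrifugation separates cells from the fluid part of blood. That is the right step when the assay is run on serum. It is the wrong step when the assay counts cells, sizes them, or reports the share of blood volume that they occupy.

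The sentence puts hematology in the same limb as immune response and so tells sites to spin both. A site that complied could produce hematology samples that the central laboratory rejects, leaving missing values, or results that do not reflect the woman's blood. Eligibility, grading and rule 2c all depend on absolute values, so they are exposed even if every group is handled alike. The Day 8 visit may be a home visit by site staff or a third party, so the written instruction matters for that draw.

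**Working it through.** No sample size, power or event rate depends on this sentence, and the protocol gives no figure to reproduce. The check sets the relevant places side by side and then counts draws.

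**1. What the sentence covers.** One verb governs both limbs: centrifuge within 1 hour for biochemistry, or within 2 hours for hematology or immune response. Hematology is named, not merely implied.

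**2. Which samples the step suits.**
- Immune response: Table 13 (Section 8.1.2) gives serum for the RSV-A, RSV-B and RSVPreF3 IgG assays. The step fits.
- Biochemistry: Table 26 (Section 10.2) lists AST, ALT, creatinine and urea nitrogen, which are dissolved constituents. The step fits.
- Hematology: Table 26 lists leukocytes, lymphocytes, neutrophils, eosinophils, platelets, erythrocytes, hematocrit, hemoglobin and MCV. These are properties of cells in unseparated blood. The step does not fit. This follows from what the parameters are, not from a figure in the protocol.

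**3. Whether anything exempts hematology.** Tables 1, 11 and 26 and Sections 8, 8.1.4 and 10.2 contain no exemption. Table 11 gives the sample type as whole blood ("Whole Blood | Hematology, Biochemistry | ~5.5 | ml | Screening"), but that label heads the whole maternal venous block, including immune-response draws that are properly spun. It describes what is drawn and settles nothing.

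**4. Whether the laboratory manual resolves it.** Section 8.1.4 requires the manual and Section 1.3 together, and Section 8 makes protocol adherence mandatory, with waivers only for immediate safety concerns. If the manual says not to spin hematology samples, it contradicts the protocol. If it repeats the protocol, the samples are at risk. The protocol sentence needs correcting in either case.

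**5. Draws affected, per vaccinated woman (Tables 1 and 11).**
- Full hematology panel: screening (1), Visit 1 (0 if the screening sample was taken no more than 15 days earlier, otherwise 1), Visit 2 (1). Total 2 to 3; at 300 women, 2 × 300 = 600 to 3 × 300 = 900.
- Hematocrit only: Visits 3, 5 and 6, so 3 × 300 = 900. These fall under the sentence but outside the baseline and Day 8 endpoint.
- All hematology draws: 5 to 6 per woman, or 1,500 to 1,800.

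These are ceilings for vaccinated women: 300 is the maximum enrolment, and an early delivery can replace Visits 2 to 4 with Visit 5. Screening draws from women who are not enrolled are not counted.

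**6. Size of the effect.** The protocol says nothing about what centrifugation does to a count or how many sites would follow the sentence literally. No change in abnormality rates can be calculated.

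**The case against.** The strongest objection is that handling is really set by the laboratory manual, with all required tests except urinalysis normally run centrally, so sites may never act on this sentence. That stands as a limit on harm. It does not clear the sentence, which is binding and would then conflict with the manual.

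Four stronger readings are tempting and are not supported:

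- **That the primary laboratory endpoint would be unreliable.** This requires literal compliance and an effect size, and the protocol shows neither.
- **That all 1,500 to 1,800 draws bear on the endpoint.** Only the 600 to 900 panel draws do.
- **That home collection puts eligibility at risk.** Section 1.3 lists maternal Visits 2, 3, 4, 7 and 8 as possible home visits. Screening and Visit 1 are not listed.
- **That artefacts would falsely trigger rule 2c.** The rule needs at least 4 subjects and at least 25% across the active groups. With 16 active recipients both conditions meet at 0.25 × 16 = 4; with 200 the second needs 0.25 × 200 = 50. The IDMC sees unblinded data and could notice the same pattern under placebo.

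It is also fair to say that handling is common to all three groups, so any artefact should not favor one. That protects between-group comparison. It does not protect eligibility or grading, and rule 2c counts active recipients only. Section 8.3.2.2 requires clinically significant abnormal values to be repeated, which would help expose false abnormalities but would not recover a rejected sample or reveal a falsely normal one.

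**Conclusion.** The instruction is wrong as written: it requires centrifugation of samples meant for a cell-based panel, and nothing in the protocol exempts them. The exposure is at most 2 to 3 endpoint-panel draws per woman (600 to 900 at 300 women), plus the Visit 3, 5 and 6 hematocrit draws outside the endpoint. Whether any result would be lost or distorted is unknown, because the laboratory manual is not shown.

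The conclusion rests on the plain reading of the sentence and on the nature of the Table 26 parameters. It looks like a drafting slip that grouped hematology with the serum samples. The point is a low-cost correction, not a demonstrated failure of the endpoint, and no design, sample size or analysis changes.

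**What to change.** Amend the Section 1.3 note so that the centrifugation times apply only to biochemistry samples (1 hour) and immune-response samples (2 hours). Add that hematology and hematocrit samples are not centrifuged and are handled as the laboratory manual directs. Leave tube type, mixing and stability limits to the manual, since the protocol gives none of these.

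Then check that the manual agrees with the amended text and notify sites, including any third party that collects blood at home visits.

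The cost is one or two sentences and a site memo, with no added women, visits or procedures.
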